## **2.5 Trial Rationale**

This trial will evaluate efficacy and safety of different vadadustat dosing strategies in hemodialysis subjects converting from ESAs to further characterize the optimal vadadustat regimen. See [Section 4.2](#) for additional rationale for the trial design elements.

Trial sites will receive updated versions of the IB when available, and trial sites should refer to the most current version as needed.

### 3 Objectives and Endpoints

Table 3-1 Trial Objectives and Endpoints	
Objectives	Endpoints

Primary: To demonstrate the efficacy and safety of vadadustat compared to darbepoetin alfa for the maintenance treatment of anemia in hemodialysis subjects after conversion from current ESA therapy.
	
Primary Efficacy: Change in Hb between Baseline (average pretreatment Hb) and the primary evaluation period (average Hb from Weeks 20 to 26, inclusive).
 
Key Secondary Efficacy: Change in Hb value between Baseline (average pretreatment Hb) and the secondary evaluation period (average Hb from Weeks 46 to 52). Other Efficacy:
 
 
• Proportion of subjects having average Hb values within the target range during the primary evaluation period (Weeks 20 to 26).
 
• Proportion of subjects having average Hb values within the target range during the secondary evaluation period (Weeks 46 to 52).
 
• Proportion of subjects receiving IV iron therapy from Baseline to Week 52.
 
• Average monthly dose of IV elemental iron administered from Baseline to Week 52 in subjects who have received IV elemental iron.
 
• Receipt of ESA rescue.
 
• Proportion of subjects receiving RBC transfusions from Baseline to Week 26.
 
• Proportion of subjects receiving RBC transfusions from Baseline to Week 52.
 
• Change from Screening Visit 2 36-Item Short Form (SF-36v2) Health-related Quality of Life (HRQOL) scores.
 
• Change from Screening Visit 2 to the average value in Anemia Subscale ("Additional Concerns") of Functional Assessment of Cancer Therapy-Anemia (FACT-An) Score.
 
• Change from Screening Visit 2 to the average value in Total FACT-An Score.
 
• Change from Screening Visit 2 in score of Patient Global Impression of Severity (PGI-S).
 

Table 3-1 Trial Objectives and Endpoints	
Objectives	Endpoints
	
 
Score of Patient Global Impression of Change (PGI-C).
 
 
Safety endpoints: AEs and SAEs, vital sign measurements, ECGs and clinical laboratory values, episodes of Hb > 12.0 g/dL, > 13.0 g/dL, or > 14.0 g/dL, and number of episodes of Hb increase > 1.0 g/dL within any 2-week interval or > 2.0 g/dL within any 4-week interval.
 
Pharmacokinetic: No PK analysis will be conducted. Vadarustat plasma concentrations may be included in a population PK analysis reported separately (Table 8.2-1).
 
Pharmacodynamic: EPO, reticulocytes, and markers of iron metabolism (iron, ferritin, TIBC, etc.).
 

[Section 9.4](#) describes the statistical analysis of the endpoints.

## 4 Trial Design

### 4.1 Type/Design of Trial

This is a phase 3b, randomized, open-label, active-controlled trial of vadarustat versus darbepoetin alfa for the maintenance treatment of anemia in hemodialysis subjects, after conversion from ESA therapy.

Following a Screening period of up to 8 weeks (56 days), subjects who meet all eligibility criteria will be randomized 1:1:1 to vadarustat QD, vadarustat TIW, or darbepoetin alfa. Target enrollment in this trial is an estimated 300 subjects at up to 150 investigative sites in the US and Europe ([Figure 1.2-1](#)).

Subjects will be randomized at the Baseline Visit using an Interactive Web Response (IWR) system to receive either vadarustat QD, vadarustat TIW, or darbepoetin alfa.

Randomization will be stratified with respect to:

- Geographic region (US versus Europe, approximately 90 subjects in Europe).
- Mean weekly darbepoetin alfa dose (or ESA equivalent) calculated over a period of 8 weeks prior to Screening Visit 2:
  - Low darbepoetin alfa dose group ( $\leq 0.45 \mu\text{g/kg/week}$ ).
  - High darbepoetin alfa dose group ( $> 0.45$  and  $\leq 1.5 \mu\text{g/kg/week}$ ).

In each stratum, there will be 3 arms: vadadustat QD, vadadustat TIW, and darbepoetin alfa.

Following screening and randomization, there will be 2 periods during the trial:

- **Conversion and Maintenance Treatment Period (Weeks 0 to 52):** conversion to investigational medicinal product (IMP) for maintaining Hb (Weeks 0 to 20), primary efficacy evaluation (Weeks 20 to 26), and secondary efficacy evaluation (Weeks 46 to 52).
- **Safety Follow-up Period (Early Termination [ET] and Follow-up):** post-treatment Safety Follow-up Visit (ET/End of Treatment [EOT] + 4 weeks) (in person).

Individual subjects will participate in total trial duration of approximately 64 weeks.

A structured exit interview may be conducted at the EOT Visit at a subset of sites. Hemoglobin will be assessed with a complete blood count (CBC) through the central laboratory for dose adjustments and efficacy and safety evaluations.

**The aim of the dosing strategy is to maintain Hb levels of 10.0 g/dL to 11.0 g/dL in the US and 10.0 g/dL to 12.0 g/dL in Europe.**

For subjects assigned to vadadustat, the initial dose of vadadustat will depend on mean weekly darbepoetin alfa dose (or equivalent) calculated over a period of 8 weeks prior to Screening Visit 2 as follows:

- Low darbepoetin alfa dose group ( $\leq 0.45 \text{ } \mu\text{g/kg/week}$ ): vadadustat 300 mg QD, 600 mg TIW.
- High darbepoetin alfa dose group ( $> 0.45 \text{ and } \leq 1.5 \text{ } \mu\text{g/kg/week}$ ): vadadustat 450 mg QD, 750 mg TIW.

Refer to the trial-specific Dosing Guideline for instructions on ESA medications conversion to an equivalent darbepoetin alfa dose for stratification and randomization.

Adjustments to doses for vadadustat will be guided by Hb concentration and Dose Adjustment Algorithms ([Section 6.1.1](#)).

For subjects who were receiving darbepoetin alfa during screening and randomized to the darbepoetin alfa treatment arm, the initial dosing regimen in the trial (starting from Baseline/Day 1) will be approximately the same weekly dose that they were receiving prior to randomization. Darbepoetin alfa dose will be administered IV at the hemodialysis clinic. For subjects receiving darbepoetin alfa for the first time, the initial dosing regimen (starting from Baseline/Day 1) will be determined by the US Package Insert (USPI) or European Union (EU) Summary of Product Characteristics (SmPC), per the medical

judgement of the investigator. Dose adjustments will be guided by the USPI or EU SmPC ([Section 6.1.1.4](#)). ESA dosing is independent of the visit schedule, and the dosing schedule may shift per local standard of care and investigator discretion.

Investigators will prescribe iron supplementation (IV, oral, or intradialytic) as needed during the trial to maintain ferritin  $\geq 100$  ng/mL or transferrin saturation (TSAT)  $\geq 20\%$  (see [Section 6.5.2.1](#) for details regarding iron supplementation during the trial). Subjects already receiving oral iron supplementation as part of their treatment plan may continue their current treatment regimen. Because of the potential for oral iron to reduce the bioavailability of vadadustat, the IMP is not to be administered concurrently with an oral iron supplement (including multivitamins containing iron), iron containing phosphate binders, or any oral medications containing iron.

Subjects will be instructed to take vadadustat at least 1 hour before oral medications containing iron ([Section 6.5.2.1](#)).

Clinical and safety assessments will be performed as indicated at Screening, during the Conversion and Maintenance Period, and during the Follow-up Period (4 weeks after the EOT) as shown in the Schedule of Assessments ([Table 1.3-1](#)).

The trial will be considered completed (end of trial) after all randomized subjects have completed their final trial visit (ET, Week 52/EOT, or Safety Follow-up) or have prematurely withdrawn from the trial (lost to follow-up). A subject is considered as having completed the trial after completion of their final trial visit (ET or Week 52/EOT). Safety Follow-up Visit data summarization and analysis will be performed separately.

## 4.2 Scientific Rationale for Trial Design

This trial will evaluate different starting doses of vadadustat based on pre-baseline ESA doses. Numerous studies have demonstrated that hemodialysis patients requiring higher ESA doses to treat their anemia have a higher burden of comorbidities, inflammation, and a greater risk of adverse outcomes. As described above ([Section 2.3](#)) in a phase 2 hemodialysis trial (AKB-6548-C1-0011), a post-hoc analysis suggested higher pre-baseline ESA doses were associated with lower observed mean Hb levels. Subjects on higher pre-baseline ESA doses may benefit from a higher starting dose of vadadustat after initial conversion from ESAs.

Two levels of pre-baseline ESA dose will be evaluated. Subjects will be randomized to one of 2 cohorts based on pre-baseline darbepoetin alfa dose ( $\leq 0.45$   $\mu\text{g}/\text{kg}/\text{week}$  and between  $> 0.45$  and  $\leq 1.5$   $\mu\text{g}/\text{kg}/\text{week}$ ) or equivalent. This dose threshold of  $0.45$   $\mu\text{g}/\text{kg}/\text{week}$  was determined by converting the ESA threshold of  $90$  U/kg/week. The ESA threshold of  $90$  U/kg/week was based on the median ESA doses reported in the US

Renal Data System and US Dialysis Outcomes and Practice Patterns Trial, which ranged from approximately 90 to 110 U/kg/week.

In this trial, darbepoetin alfa was chosen as an active comparator as it is marketed and available globally and has an extensive safety profile. This is particularly relevant in the current medical and regulatory climate given the accumulating trial findings that resulted in the FDA revising the prescribing information for the currently marketed ESAs. These trial results indicate an increased risk of death and adverse CV events, such as stroke and HF, particularly when using ESAs to achieve a higher Hb concentration. In addition, post-hoc analysis has also shown that higher ESA doses carry a higher risk for CV outcomes regardless of Hb. In the US, the mortality and CV risks associated with ESAs are outlined in a boxed warning in the prescribing information of ESAs, with a recommendation to use the lowest dose possible to avoid transfusions. While no similar major warnings exist in the EU SmPC, there is caution suggested with use of ESAs, and recommendation to keep Hb levels below 12.0 g/dL. Recent clinical practice guidelines recommend that risk factors for stroke and malignancy should also be taken into account when making treatment decisions to use ESAs for the treatment of anemia.

This trial incorporates an approach to vadadustat dose adjustment designed to maximize the probability that Hb can be maintained within the target range of 10.0 to 11.0 g/dL in the US and 10.0 to 12.0 g/dL in Europe, inclusive (see [Section 6.1.1.1](#)). The approach to vadadustat dose adjustment in this phase 3b trial includes several modifications as compared to the vadadustat dosing algorithms used in previously completed phase 2 studies and the dosing algorithm used in the ongoing phase 3 studies.

During this trial, dose increases for vadadustat will be allowed at 4-week intervals, with the exception of the initial 2 weeks of treatment. An additional dose increase may occur after 2 weeks of treatment initiation based on the Hb trajectory, in the daily and TIW dosing arms, in subjects with a Hb decline  $\geq 0.5$  g/dL from Baseline/Day 1 to Week 2 following conversion from prior ESA and if Hb is  $< 10$  g/dL. This approach is commonly used in clinical practice to treat patients with declining or low Hb values. Risk of abrupt or excessive increases in Hb is minimized due to the underlying Hb trajectory and is further mitigated by close Hb monitoring.

This trial will evaluate efficacy and safety of different vadadustat dosing strategies in hemodialysis subjects converting from ESA to further characterize the optimal vadadustat regimen. This trial will be performed as an open-label trial. Because Hb values are objective and will be measured via a central laboratory for all efficacy endpoints, efficacy assessments are not considered to be subject to bias with an open-label design.

#### 4.3 Dosing Rationale

In this trial, vadadustat starting daily doses will be determined by pre-baseline ESA dose ([Section 6.1.1.1](#)). In this trial starting doses of vadadustat will be 300 mg QD or 600 mg TIW in subjects converting from darbepoetin alfa doses  $\leq 0.45 \mu\text{g/kg/week}$  (or ESA equivalent) and 450 mg QD and 750 mg TIW in subjects converting from darbepoetin alfa doses  $> 0.45$  and  $\leq 1.5 \mu\text{g/kg/week}$  (or ESA equivalent).

The maximum vadadustat dose evaluated in completed phase 1 studies in healthy subjects was 1200 mg (single dose) and 900 mg (10 days). Vadadustat 750 mg and 900 mg QD as titration doses are being studied in an ongoing phase 2 trial in DD-CKD subjects and in an ongoing phase 1b trial, DD-CKD subjects have been dosed 900 mg QD. As described above ([Section 2.3](#)), the maximum vadadustat starting dose evaluated in completed phase 2 NDD-CKD studies was 630 or 600 mg QD, and in completed phase 2 DD-CKD studies was 450 or 600 mg.

Based on the dosing algorithm, vadadustat will be titrated to achieve and maintain Hb levels within the target range of 10.0 to 11.0 g/dL, inclusive in the US and 10.0 to 12.0 g/dL inclusive in Europe. The dose range for titration is 150 to 900 mg QD and 150 to 1200 mg TIW.

Doses of 150 to 630 mg QD have been evaluated in studies evaluating subjects with NDD-CKD and DD-CKD. Evaluation of higher doses is justified because dose-ranging clinical studies have not identified a vadadustat dose at which a plateau in exposure or effect has been observed. In phase 1 studies in healthy subjects, dose-proportional increases in AUC and  $C_{\max}$  and dose related increases in serum EPO were observed up to the maximum doses studied, single doses of 1200 mg and multiple doses of 900 mg daily for 10 days. In phase 2 studies in anemic NDD-CKD and DD-CKD subjects, dose-dependent increases in Hb were observed up to the maximum dose studied of 600 or 630 mg daily. It is anticipated that daily doses of vadadustat at 750 or 900 mg, which yield an increase in systemic exposure above 600 mg of approximately 25% and 50%, respectively, would yield an incremental erythropoietic effect greater than 600 mg for the treatment of anemia associated with CKD.

As described above ([Section 2.3](#)), the 16-week phase 2 hemodialysis trial evaluated hemodialysis subjects switching from ESA to vadadustat 450 mg TIW for an 8-week fixed-dose period followed by 8 weeks of dose adjustment according to Hb response. The TIW dosing regimen of 450 mg TIW maintained Hb levels through 16 weeks, similar to 300 mg or 450 mg QD dosing regimens. However, six of the 31 patients in TIW arm were withdrawn from the trial because of worsening of anemia. Upon further analysis of

these patients, it was observed that these patients had higher baseline-ESA doses. It is postulated that these patients could have benefited with higher TIW starting and maximum dose of vadadustat to yield an increase in erythropoietic effect to overcome worsening of anemia. To maximize the probability that subjects treated with vadadustat TIW will maintain Hb levels within the target range, this trial will allow for earlier dose increase after 2 weeks of initial treatment and permit dose increases up to 1200 mg TIW.

The maximum dose of vadadustat in this trial is 900 mg daily and 1200 mg TIW. No accumulation was evident after repeat dosing with vadadustat exposure and therefore, the exposures with 1200 mg single dose was likely to be similar to 1200 mg TIW. Per total weekly dosing, 1200 mg TIW (3600 mg/week) is a lower dosing regimen compared 900 mg QD (6300 mg/week) and no  $C_{max}$  related AEs were evident throughout clinical development of vadadustat.

From a safety and tolerability standpoint, as described above (Section 2.3), multiple doses of 700 and 900 mg daily for up to 10 days and single doses of 1200 mg have been examined in healthy subjects. Vadadustat demonstrated dose-proportional PK and achieved serum EPO concentrations up to 34.4 mIU/mL, levels considered physiologic and below exposures achieved with injectable ESAs. A higher incidence of AEs in the gastrointestinal SOC (nausea, diarrhea, abdominal pain, dyspepsia) was observed in groups treated with 700, 900, or 1200 mg compared with lower vadadustat doses or placebo. Most AEs were mild to moderate, short-lived (1 or 2 days), and assessed as unrelated by investigators. No AEs led to trial withdrawal, and no SAEs were reported. No clinically meaningful changes or abnormalities in vital signs, safety laboratory studies, or ECG parameters were reported.

The starting dose of vadadustat for the high darbepoetin alfa group TIW arm will be 750 mg and for the low darbepoetin alfa TIW arm will be 600 mg. In the ongoing global phase 3 program, subjects are getting higher total weekly doses as subjects treated in the high darbepoetin alfa group may be administered 600 mg vadadustat daily for a total weekly dose of 4200 mg; no significant dose-related safety concerns have been identified by the Independent Data Monitoring Committee (IDMC) in these trials.

Assessment of animal-to-human safety margins is presented in the IB.

Intensive Hb monitoring, a strict dose adjustment algorithm, and phlebotomy will be implemented to mitigate the potential risk of a rapid Hb rise, as follows:

- Hb measurements are scheduled at least every 2 weeks to Week 20.
- The dose adjustment algorithm will target a narrow Hb range, 10.0 to 11.0 g/dL in the US and 10 to 12 g/dL in Europe.

- The protocol specifies that phlebotomy may be considered in the setting of high Hb levels ( $> 14.0$  g/dL) or a high Hb rate of rise, based on the investigator's judgment.

Phase 2 studies demonstrated that cessation of treatment resulted in prompt reduction in mean Hb within 2 to 4 weeks.

#### **4.4 End of Trial Definition**

The end of trial date is defined as the last date of contact or the date of final contact attempt from the safety follow-up electronic case report form (eCRF) page for the last subject completing or withdrawing from the trial.

The trial will be considered completed (end of trial) after all randomized subjects have completed their final trial visit (ET, Week 52/EOT, or Safety Follow-up).

#### **4.5 Definition of Completed Subjects**

A subject will be considered as having completed the trial after completion of their final trial visit (ET, or Week 52/EOT). Safety Follow-up Visit data summarization and analysis will be performed separately.

Subjects who discontinue prematurely from the trial will complete the ET Visit assessments and will complete the Safety Follow-up Visit, 4 weeks after their last dose of IMP.

The need for rescue therapy does not constitute trial completion unless it meets the criteria stated in [Section 7.3.2](#). Also, the occurrence of a safety endpoint does not constitute trial completion and is not a criterion for subject withdrawal from the trial or IMP (vadadustat or darbepoetin alfa).

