**Trial Duration:**

Each subject in this trial is expected to participate in the following periods of the trial (approximate durations listed):

[figure not shown]
- Two Screening Visits (Screening Visit 1 and Screening Visit 2) (Weeks -8 to 0)
- Baseline/Randomization Visit (Week 0/Day 1)
- Treatment Period (Conversion and Maintenance) Trial Visits/Evaluations while receiving IMP: Weeks 2, 4, 6, 8, 10, 12, ( $\pm 3$  days) 16, 20, 24, ( $\pm 5$  days), 26 ( $\pm 3$  days), 30, 34, 38, 42, 46, 50, ( $\pm 5$  days) 52/EOT ( $\pm 3$  days).
- ET Visit (+ 7 days)
- Follow-up Visit/EOT (4 weeks after the ET [+ 7 days] visit).
- Unscheduled visit(s)

**Trial Completion:** The trial will be considered completed after all randomized subjects have completed their final trial visit (ET, Week 52/EOT, or Safety Follow-up).

**Subject Completion:** A subject will be considered as having completed the trial after completion of their final trial visit (ET or Week 52/EOT). Safety Follow-up Visit data summarization and analysis will be performed separately.

The trial duration for an individual subject from the time the informed consent form (ICF) is signed to the final subject assessment is expected to be approximately 64 weeks.

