## **7.3 Individual Subject Discontinuation**

During this trial, it is anticipated that some subjects may permanently discontinue IMP (vadadustat or darbepoetin alfa).

Subjects who discontinue IMP prematurely and the investigator determines that the subject will be permanently discontinued from the trial (see [Section 7.3.1](#)), will complete the ET Visit assessments and the Safety Follow-up Visit, 4 weeks after ET Visit.

Subjects may discontinue prematurely from the trial for any of the following reasons:

- Adverse Event.
- Subject withdrawal of consent.
- Investigator's discretion.
- Lack of efficacy, defined as inadequate response to darbepoetin alfa or vadadustat in the investigator's opinion.
- Lost to follow-up despite reasonable efforts by the investigator to locate the subject.
- Receipt of a solid organ (including kidney), hematopoietic stem cell, or bone marrow transplantation.
- Meeting criteria for Trial Medication Stopping Rules (see [Section 7.3.2](#)).
- Change in dialysis modality (ie, from hemodialysis to peritoneal dialysis or change from in center hemodialysis to home/nocturnal hemodialysis).
- Permanent change in frequency of in-center hemodialysis from three-times per week.
- Death.
- Other reasons (pregnancy [see [Section 10.3](#)], specific reasons to be documented by the investigator).

A subject has the right to withdraw consent for participation in the trial at any time ([Section 7.3.4](#)).

See [Table 7.3.2-1](#) for additional details on the management of subjects with ALT and AST abnormalities.

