### 7.3.2 Treatment Discontinuation

After treatment assignment, a subject may stop treatment permanently for a variety of reasons. Treatment discontinuations may be initiated by a subject who is not satisfied with treatment or may become medically necessary due to AEs, required treatment with a disallowed medication or therapy, or other issues, as determined by the investigator.

However, each investigator must comprehensively review the circumstances and offer the subject options for continued treatment to the degree possible. If, after discussion with the investigator about possible mitigations for AEs, etc., the subject still chooses to discontinue IMP, the subject will permanently discontinue IMP and will complete the ET Visit assessments and will complete the Safety Follow-Up Visit, 4 weeks after last dose of IMP and the subject will not be allowed to re-start the IMP.

Trial medication is to be permanently discontinued if ESA rescue (other than darbepoetin alfa in comparator arm, any ESA in vadadustat arm) is not in the setting of acute bleeding (ie, gastrointestinal bleed, surgery, excess bleeding) and one of the following:

- The first cycle of ESA rescue lasts >30 days or
- Subject requires a second cycle of ESA for rescue (that must be related to anemia) at any time.

Trial medication must be permanently discontinued if a subject meets one of the criteria in [Table 7.3.2-1](#).

Table 7.3.2-1 Trial Medication Stopping Rules	
ALT or AST > 3x ULN and total bilirubin > 2x ULN	Permanently Discontinue Treatment
ALT or AST > 3x ULN and INR > 1.5	Permanently Discontinue Treatment
ALT or AST > 8x ULN	Permanently Discontinue Treatment
ALT or AST remains > 5x ULN over 2 weeks a	Permanently Discontinue Treatment
ALT or AST > 3x ULN with symptoms including eg, fatigue, nausea, vomiting, right upper quadrant pain, fever, rash or eosinophilia	Permanently Discontinue Treatment

INR: international normalized ratio; ULN: upper limit of normal

aRe-challenge generally should be avoided with ALT or AST > 5x ULN unless there are no other good therapeutic options.

See [Section 8.8](#) for reporting requirements related to a subject being permanently discontinued based on meeting the laboratory abnormalities list above in [Table 7.3.2-1](#).

For subjects who permanently discontinue IMP, the investigator will resume standard of care treatment, including ESAs and iron therapy, as deemed appropriate.

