### **Follow-up Visit**

The Follow-up Visit will be conducted 4 weeks after the EOT Visit, or 4 weeks after the last dose of IMP for ET.

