Section 6.5.2.2 (Phosphate Binders)	Clarified that subjects will be instructed to take vadadustat at least 1 hour before or 2 hours after non-iron-containing phosphate binders.
Table 6.5.2.3-1 (Results and Management of Concomitant Administration of Vadadustat with Statins)	Clarified guidance on inhibitor potency.
Section 7.3 (Individual Subject Discontinuation)	Clarified that subjects who discontinue IMP prematurely and the investigator determines that the subject will be permanently discontinued from the trial will complete the ET Visit assessments and the Safety Follow-up Visit, 4 weeks after ET Visit.

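### Early leavers' Safety Follow-up Visit is timed from the last dose in three protocol sections and from the ET visit elsewhere; after a full 30-day interruption the last-dose rule makes it due before ET

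*Protocol*

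**What the plan says.** Three places in the current protocol time the visit from the last dose of study drug:

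- Section 4.5, for everyone who leaves the trial prematurely: "will complete the Safety Follow-up Visit, 4 weeks after their last dose of IMP".
- Section 7.3.2, for subjects who choose to stop treatment: "will complete the Safety Follow-Up Visit, 4 weeks after last dose of IMP".
- Section 8, Follow-up Visit, which sets 4 weeks after EOT for completers, "or 4 weeks after the last dose of IMP for ET".

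Other places time it from the ET visit:

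- Section 7.3, for "Subjects who discontinue IMP prematurely and the investigator determines that the subject will be permanently discontinued from the trial" (with a cross-reference to Section 7.3.1): they "will complete the ET Visit assessments and the Safety Follow-up Visit, 4 weeks after ET Visit".
- Synopsis, Trial Duration: "Follow-up Visit/EOT (4 weeks after the ET [+ 7 days] visit", with the ET visit itself listed as "ET Visit (+ 7 days".
- The synopsis Trial Design text, the Schedule of Assessments, Protocol Section 4.1 and SAP Section 2.2 all give ET/EOT plus 4 weeks. SAP Table 1 (Section 5.1) accepts follow-up data from 15 to 42 days after ET/EOT.

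Two further provisions matter. Section 7.3.1 lets treatment be interrupted for up to 30 days; a subject not restarting by Day 30 is discontinued and then has the ET and Safety Follow-up visits. Section 8 asks for ET assessments within 7 days of stopping study drug.

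**The concern.** Sections 4.5 and 7.3 cover the same people, those who leave early, and give them different due dates for the same visit. The protocol has no rule on which sentence prevails. The SAP's statement that its methods override the protocol concerns analyses, not visit scheduling.

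The last-dose rule also fails on a route that the protocol itself creates. When an interruption runs its full length, the ET visit comes about a month after the last dose, so a follow-up visit timed from that dose falls due first. ESA rescue can lead there: study drug is interrupted during rescue (Sections 6.5.3.2 and 7.3.1), and outside acute bleeding a first rescue cycle of more than 30 days requires permanent discontinuation (Section 7.3.2).

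AE collection runs through the Safety Follow-up Visit (Sections 8.8 and 8.8.2.1), so its closing date depends on which sentence a site follows. With up to 150 sites, practice could vary.

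**Working it through.** There is no plan figure to reproduce; the check is a day count.

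**Inputs.** Four weeks is 28 days. Maximum interruption is 30 days (Section 7.3.1). The ET visit is held within 7 days of stopping (Section 8). The SAP follow-up window is ET+15 to ET+42 days (SAP Table 1).

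**Assumptions.** The last dose is Day 0 and any interruption starts that day. After a failed interruption, the 7-day ET window runs from the Day-30 decision, so ET falls on Day 30 to 37. For three-times-weekly vadadustat or darbepoetin alfa, the last dose may come some days before the first missed one, which would lengthen the gap.

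**Formulas.** Let d be the days from last dose to ET.

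- Last-dose rule: due Day 28, which is 28 − d days after ET.
- ET rule: due Day d + 28.
- AEs are also assessed at ET, so routine collection ends at max(28, d) under the first rule and at d + 28 under the second. The difference is min(d, 28).

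| d | Last-dose rule: due | Relative to ET | ET rule: due | Difference in AE collection (days) | Last-dose visit in SAP window? |
|---|---|---|---|---|---|
| 0 | Day 28 | ET+28 | Day 28 | 0 | yes |
| 7 | Day 28 | ET+21 | Day 35 | 7 | yes |
| 13 | Day 28 | ET+15 | Day 41 | 13 | yes |
| 14 | Day 28 | ET+14 | Day 42 | 14 | no |
| 30 | Day 28 | ET−2 | Day 58 | 28 | no |
| 37 | Day 28 | ET−9 | Day 65 | 28 | no |

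The order of the visits reverses whenever d exceeds 28. An ET visit on Day 30 itself is already 2 days late relative to the Day-28 due date, so the reversal does not depend on the ET window.

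**With a +7-day allowance on follow-up, used in full (Day 35).** d = 20 gives ET+15 (in the SAP window); d = 21 gives ET+14 (out); d = 30 gives ET+5; d = 35 gives the same day as ET; d = 37 gives ET−2. After a full interruption the visit still misses the SAP window.

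**Alternative reading of stopping.** If the 7-day ET window ran from the last dose, ET would be due by Day 7, before Section 7.3.1 requires the restart decision. That does not remove the conflict.

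**The case against.** The strongest reply is that the protocol already points to the right rule. Section 8 opens by directing sites to the Schedule of Assessments for timing, and the Schedule says ET/EOT plus 4 weeks. For an interruption that ends in discontinuation, Section 7.3 cross-refers to 7.3.1 and gives the ET anchor, while Section 7.3.2 does not clearly reach that subject. The Amendment 1 log, which matches current Section 7.3, points the same way: "permanently discontinued from the trial will complete the ET Visit assessments and the Safety Follow-up Visit, 4 weeks after ET Visit". This makes confusion less likely. It does not settle the matter, because the last-dose rule also stands in Section 8, in the paragraph that describes this very visit.

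Nor is the reversal inevitable. Section 7.3.1 asks for the restart decision before the 30 days are up, and an early decision can put ET before Day 28. If the +7-day allowance covers follow-up, a Day-35 visit would fall on or after an ET held on Day 30 to 35; for outright stops, one visit could then satisfy both rules. These limits stand. But Section 7.3.1 still permits Day 30, and the nominal due date is still Day 28.

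The objection that little follows from this is largely right. Visits continue during an interruption. Later AEs judged related to study drug are still reported (Section 8.8.2.1), and SAEs and related AEs are followed beyond the visit (Sections 8.8 and 8.8.4). The SAP's AE summaries (Section 10.3) apply no follow-up cut-off, and no named analysis is shown to change because a visit falls outside the ET+15 to ET+42 window.

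**Conclusion.** The contradiction is real and lies in current text; it does not rest on the amendment log. Due dates differ by 0 to 7 days for outright stops and by 30 to 37 days after a full interruption, where the last-dose rule puts follow-up 2 to 9 days before ET. These figures rest on the interruption starting at the last dose and on ET being held within 7 days of the Day-30 decision.

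The effect is minor. What can be lost is routine collection of new, unrelated AEs arising more than 28 days after the last dose, for up to 28 days. The documents give no frequency for this route and no reason to expect a difference between arms; Protocol Section 9.3 says only that up to 30% of subjects may discontinue for any reason. The primary hemoglobin analysis is unaffected. This is a worthwhile wording correction, not a threat to the trial's conclusions.

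**What to change.** In Section 4.5, Section 7.3.2 and the Follow-up Visit paragraph of Section 8, replace the last-dose timing for early leavers with 4 weeks after the ET visit, as in Section 7.3 and the synopsis. Add a sentence stating that this also applies when an interruption ends in discontinuation. Follow-up would then always come after ET, with its due date inside the SAP window, and routine AE collection would end by one rule.

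The cost is three wording edits and the clarifying sentence, with no added visit and no SAP change. For sites now using the last-dose sentences, follow-up moves later by the gap between last dose and ET: 0 to 7 days for outright stops, up to 30 to 37 days after a full interruption. By then such subjects may be back on standard-of-care ESAs, so some of the extra events collected may reflect that treatment.
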